CDF	Cumulative Distribution Function
DCE	Dynamic Contrast Enhanced
DLCO	Diffusing Capacity of the Lung for Carbon Monoxide
DLNO	Diffusing Capacity of the Lung for Nitrous Oxide
ECG	Electrocardiogram
eGFR	Estimated Glomerular Filtration Rate
FENa	Fractional excretion of sodium
GSK	GlaxoSmithKline
HF	Heart Failure
HV	Healthy Volunteers
ICH	International Conference on Harmonisation
Kg	Kilogram
Ktrans	Exchange Rate
MedDRA	Medical Dictionary for Regulatory Activities
mL	Milliliter
MRI	Magnetic Resonance Imaging
NO	Nitric Oxide
NT-proBNP	N-terminal of pro-Brain-type Natriuretic Peptide
NYHA	New York Heart Association
RAP	Reporting and Analysis Plan
RBC	Red Blood Cells
RER	Respiratory Exchange Ratio
RPE	Rating of Perceived Exertion
SAE	Serious Adverse Event
SPM	Study Procedures Manual
TRPV4	Transient Receptor Potential Vanilloid 4
VCO ₂	Volume of Carbon Dioxide
Ve	Interstitial Volume
VO ₂	Volume of Oxygen
Vp	Plasma Volume
WBC	White Blood Cells

Trademark Information

Trademarks of the GlaxoSmithKline group of companies	Trademarks not owned by the GlaxoSmithKline group of companies
NONE	SAS

1. INTRODUCTION

The purpose of this reporting and analysis plan (RAP) is to describe the analyses to be included in the Clinical Pharmacology Study Report for Protocol MRI201137.

Revision Chronology:		
2013N186309_00	2014-FEB-04	Original
2013N186309_01	2014-APR-24	Amendment No.: 01 This protocol amendment clarifies the exercise protocol to be conducted, details measures for endpoints, defines the biomarker to be measured (NT-pro BNP), reduces total blood volume to be collected, updates study schematic, adds an interim review of the data, removes collection of AEs as there is no IP included in the study, alters physical exams to brief physical exams, and adds a dyspnoea scale and the Borg Rating of Perceived Exertion.
2013N186309_02	2015-FEB-16	Amendment No.: 02 This protocol amendment changes modifies inclusion criteria, clarifies the exercise protocol, and corrects the footnote numbering in the time and events table.
2013N186309_03	2016-APR-08	Amendment No. 3 adds an evaluation of an additional group of subjects who have been hospitalized for acute decompensated heart failure to determine whether DCE-MRI can detect changes in measures of pulmonary oedema with standard of care treatment. Details for summarizing data from ADHF patients (referred to in this document as group 3) can be found in Section 10.2.6.
2013N186309_03	2016-APR-20	The data analysis for Group 3 has been simplified due to limited number of subjects (n=3) in the study

In addition to following the revision chronology of the study protocol, current reversions are also under the general guidance of “driving efficiency in Clinical Statistics” initiative,

and the outputs are simplified to match with the scale and lack of investigational drug of the study.

All decisions regarding final analysis, as defined in this RAP document, have been made prior to Database Freeze of the study data. After completion of 12 evaluable subjects, an informal interim look will be performed.

2. STUDY OBJECTIVE(S) AND ENDPOINT(S)

2.1. Study Objective(s)

The objectives and endpoints for the study are summarized in the table below:

Objectives	Endpoints
Primary	

 Establish whether DCE-MRI can detect differences in measures of pulmonary oedema or vascular permeability between HF and healthy volunteers (HV) groups. Explore the effect of exercise on DCE-MRI measures of pulmonary oedema and vascular permeability in HF and HV groups. Explore the effect of standard of care treatment on DCE-MRI measures of pulmonary oedema and vascular permeability in patients with ADHF. 	
 Interstitial volume (ve) and exchange rate (ktrans) measured using DCE-MRI in HF patients and HVs at baseline. Change in interstitial volume (ve) and exchange rate (ktrans) measured using DCE-MRI in HF patients and HVs before and following exercise. Change in interstitial volume (ve) and exchange rate (ktrans) measured using DCE-MRI in patients with ADHF during hospitalization and following the resolution of pulmonary oedema.
Secondary	

 Estimate the intra subject variability of DCE-MRI measures of pulmonary oedema and vascular permeability. 	
 Estimation of the variability in the interstitial volume (ve) and exchange rate (ktrans) within HF patients and HVs between 2 MRI visits approximately 1 week apart.

Objectives	Endpoints

Exploratory
 
 Explore the relationship between DCE-MRI measures of pulmonary physiology and disease severity, symptoms, pulmonary function, volume status and renal function Estimate differences in plasma volume and MR physical properties influenced by the tissue microenvironment relaxation rate, and proton density between HF and HV groups as measured using DCE-MRI Explore the distribution of DCE-MRI measures of pulmonary physiology in HF and HV groups both before and after exercise Explore the effect of standard of care treatment on plasma volume and MRI physical properties influenced by the tissue microenvironment relaxation rate, and proton density in patients with ADHF. Explore the effect of standard of care treatment on ultrasound measures of pulmonary oedema in patients with ADHF. Explore the distribution of DCE-MRI measures of pulmonary physiology in ADHF patients both before and after standard of care treatment; 	
 Correlation of MRI measures with clinical and biochemical measures: dyspnoea score, respiratory rate, NT-proBNP, exercise capacity (including BORG RPE, heart rate, blood pressure and gas exchange endpoints such as peak VO₂, Ve/VCO₂ slope), DLCO, DLNO, body weight, urine specific gravity, fractional excretion of sodium (FENa), blood urea to creatinine ratio. Plasma volume (vp), T1 relaxation rate, and proton density measured using MRI in HF patients and HVs. Interstitial volume (ve) and exchange rate (k_{trans}), and other clinical and biochemical measures as listed above if data permit. Change in Plasma volume (vp), T1 relaxation rate, and proton density measured using MRI in patients with ADHF during hospitalization and following the resolution of pulmonary oedema; Change in B-lines measured using ultrasound in patients with ADHF during hospitalization and following the resolution of pulmonary oedema; Interstitial volume (ve) and exchange rate (k_{trans}), and other clinical and biochemical measures as listed above if data permit;

3. STUDY DESIGN

[figure not shown]
The study will enroll 12 HV and 12 HF patients. First, the DCE-MRI markers of vascular permeability and pulmonary edema will be measured in HV and HF patients at rest to determine whether there is a difference between the two populations. Next, exercise-induced changes relative to rest in interstitial volume and exchange rate will be evaluated in both HV and HF patients. Since exercise increases pulmonary vascular pressure more markedly in patients with left ventricular failure as compared to normal subjects, a greater increase in vascular permeability and pulmonary oedema may be observed in patients with HF as compared to HV.

The study consists of four visits. The first visit will be a Screening Visit during which the subjects will be assessed for their tolerance of lying flat and baseline information will be collected. Within 35 days, subjects will return for the first of two scanning sessions approximately one week apart to determine baseline levels and within subject variability. A third imaging visit will incorporate a bicycle exercise challenge prior to imaging and will occur approximately one to three days after the second imaging session.

All MRI data will be anonymized at site and transferred to Bioxydyn Limited for DCE-MRI data analysis. The 'extended Tofts' tracer kinetic model will be applied to the data to provide measurements of k^{trans} (capillary transfer coefficient of contrast agent - /min), v_e (leakage space - fraction) and v_p (plasma volume - fraction). Median values of k^{trans} and v_e will be provided from each lung (total lung, apical and basal) as well as total lung for subsequent statistical analysis. All values will be corrected for the individual's hematocrit value. If not available, a typical hematocrit value will be assumed.

In Session 3 (which will be conducted in 2 visits), subjects will perform two exercise tests. Subjects will first be asked to perform a maximal exercise test limited by dyspnoea or fatigue on a cycle ergometer. At the 2nd visit, subjects will be asked to perform cycle exercise for 10 minutes at 75%-80% of the peak work rate achieved during the maximal exercise to exhaustion test described above.

For subjects with ADHF (Group 3), the study design is shown below:

4. PLANNED ANALYSES

4.1. Interim Analyses

After 12 evaluable subjects (6 HV and 6 HF patients) have completed Sessions 1 and 2, an interim review will be performed. Following the interim review, the study team will decide whether to (a) terminate the study if it is determined that the image quality is poor

(e.g., due to excessive movement during scanning or related to specifics around lung tissue) or the procedures are not well tolerated in the HF group (e.g., inability to lie flat for the duration of the imaging session), or (b) continue the study and enrol an additional 12 evaluable subjects (6 HV and 6 HF patients).

The interim decision will be based on the expert opinion of the Investigator in consultation with the GSK Study Team based on the totality of the data. No formal interim analysis will be reported out.

4.2. Final Analyses

The final planned analyses will be performed after all subjects have completed the study and after database freeze. See Section 9 to Section 10 for all final planned analyses for this study.

5. ANALYSIS POPULATIONS

An evaluable subject is defined as a subject that has MRI data of sufficient quality to enable DCE-MRI modelling in both Session 1 and Session 2.

All enrolled population

The all enrolled population will include all subjects who have signed the informed consent for participation in the study.

Safety population

The safety population will include all enrolled subjects who have initiated Session 1 DCE-MRI scan. All safety analyses will be based on the safety population.

For Group 3, the safety population will include all enrolled subjects who have initiated at least one session of DCE-MRI or LUS scan.

This is the population to be used for all tables, listings, and figures of patients in group 3.

Evaluable population

The evaluable population will include subjects in safety population who are 40 years and older. There is no plan to exclude subjects with major or minor protocol deviations from the analyses. However, subject data will be examined for evidence of protocol deviations in order to assess how well the protocol was followed. If necessary, any decision to exclude any subject from the planned analyses will be determined when the database is released for reporting purposes.

The evaluable populations have been changed in this RAP amendment to limit the analysis populations to subjects with age greater than 40 years old at baseline. At the interim analysis, it was realized that age may confound the results in the HV population. Since HV and HF subjects were not age-matched, limiting the analysis population to similar age range will provide a more appropriate comparison. This analysis will exclude

4 subjects; however, the study has enrolled an additional 5 subjects who are >40 years old in order to have a sufficient number of subjects for comparison. However, in addition to the comparisons using the defined populations in this RAP, a sensitivity analysis for the comparison between two groups on the change from baseline in V_e will be performed using safety population with all subjects who have evaluable MRI data in either Sessions 1 or 2.

The evaluable population definition does not apply to ADHF patients to be included in group 3 summaries.

This population is not applicable to Group 3.

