4.2.1.2. Inclusion Criteria for Healthy Volunteer Group (Group 1)

1. Healthy as determined by a responsible and experienced physician, based on a medical evaluation including medical history, brief physical examination, clinical laboratory tests, and ECG

4.2.1.3. Inclusion Criteria for Both the Healthy Volunteer and Heart Failure Groups (Group 1 and 2)

1. Males or females over 18 years of age at the time of signing the informed consent
2. Body weight \geq 50kg and BMI within the range 18-40 kg/m² (inclusive)
3. Able to understand and comply with protocol requirements, instructions and protocol-stated restrictions and is willing to take part in the imaging sessions
4. Capable of giving written informed consent, which includes compliance with the requirements and restrictions listed in the consent form

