7.5. Derived and Transformed Data

MRI measures: Median values of k^{trans} , v_e and v_p from multiple images/regions will be calculated for total lung, each lung (left and right) and different lung segments. For each MRI measure parameter there are 7 measurement regions: total lung, left lung, right lung, apical left segment, apical right segment, basal left segment and basal right segment for each MRI measure parameter.

Laboratory Data: The majority of laboratory results will be recorded under a numeric field. Some results may be recorded under a character field where a numeric component

(x) has been preceded by ‘>’ or ‘<’ indicating the true value of x is greater than or less than that given.

To ensure this data is not excluded from any summaries or analysis, any laboratory results recorded as ‘>x’ will be moved to the numeric field with a value of x, similarly results recorded as ‘<x’ will be moved to the numeric field with a value of x. All listings will present the data as recorded.

Age (years): Age will be calculated using the date of the screening visit relative to year of birth, according to the Integrated Data Standard Library (IDSL). In this calculation, date of birth will be imputed based on the assumption that all subjects were born on the 30th June (30 Jun YYYY).

Body Mass Index (BMI) (kg/m²): equals (weight (kg)) / ((height (m))²)

Study Day: Study day will be defined in reference to the DCE-MRI scan date in the corresponding Session. Session 1 – Day 1 will be the DCE-MRI scan date in Session 1, and Session 2 – Day 1 will be the DCE-MRI scan date in Session 2, etc.

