8.2. Demographic and Baseline Characteristics

Demography data will be summarized for safety population in this study. Disease characteristics data will also be summarized for the HF patients if data are available

These will include the following:

- Year of birth

- Gender
- Race and ethnicity
- Significant past medical history including onset, aetiology, and results of any recent relevant investigations of heart failure, as applicable
- Medication history
- Confirm heart failure class (HF patients only)
- Onset and type of symptoms (HF patients only)
- Years since diagnosis of HF (HF patients only)
- Degree of exercise intolerance-- distance/ stairs/time prior to breathlessness
- Presence of orthopnoea and/or paroxysmal nocturnal dyspnoea
- Peripheral oedema—level above ankle, non-dependent limb

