10.1. Primary Objectives

10.1.1. Baseline and post exercise Analysis

For the primary endpoints, contrast agent interstitial volume (v_e) and exchange rate (k^{trans}) data for total lung, left and right lung, apical segments and basal segments for each lung (total 7 measurements for each parameter) will be fitted separately using a repeat measure ANOVA model with terms include patient population (HF or HV), visit (i.e. sessions), interaction of patient population and visit, with subject ID as block of the repeat factor. Point estimates and associated 95% confidence intervals (CI) will be constructed to provide a plausible range of values for the following parameters of interest: mean DCE-MRI measurements in HV and HF patients, and the mean difference between the HV and HF groups, at each session, as well as the differences among MRI sessions within each patient population group (HV or HF) See example sas codes below.

```
/* analysis of primary endpoints to compare HF vs HV with Sessions 1 to
3 data */
proc mixed data=mri;
  class subjid atrtgrp visit;
  model mriresn = visit atrtgrp visit*atrtgrp/e3 ddfm=kr outp=pred_one;
  repeated visit/ subject=subjid type=un;
  by mritstu regint;
  LSMEANS visit*atrtgrp /CL ALPHA=0.05;
  estimate 'HF - HV at Session 1' atrtgrp 1 -1
           visit*atrtgrp 1 0 0 -1 0 0/cl alpha = 0.05;
  estimate 'HF - HV at Session 2' atrtgrp 1 -1
           visit*atrtgrp 0 1 0 0 -1 0/cl alpha = 0.05;
  estimate 'HF - HV at post excercise' atrtgrp 1 -1
           visit*atrtgrp 0 0 1 0 0 -1/cl alpha = 0.05;
  estimate 'Session 2 - Session 1 in HF' visit -1 1 0
           visit*atrtgrp -1 1 0 0 0 0/cl alpha = 0.05;
  estimate 'post excercise - Session 1 in HF' visit -1 0 1
           visit*atrtgrp -1 0 1 0 0 0/cl alpha = 0.05;
  estimate 'change from baseline estimates in HF' visit 0 -1 1
           visit*atrtgrp 0 -1 1 0 0 0/cl alpha = 0.05;
```

```

estimate 'Session 2 - Session 1 in HV' visit -1 1 0
           visit*atrtgrp  0 0 0 -1 1 0/cl alpha = 0.05;
estimate 'post excercise - Session 1 in HV' visit -1 0 1
           visit*atrtgrp  0 0 0 -1 0 1/cl alpha = 0.05;
estimate 'Change from baseline estimates in HV' visit 0 -1 1
           visit*atrtgrp  0 0 0 0 -1 1/cl alpha = 0.05;
estimate 'HF vs HV of Change from baseline '
           visit*atrtgrp  0 -1 1 0 1 -1/cl alpha = 0.05;

ods output lsmeans = lsm;
ods output covparms = cov_one;
ods output estimates = est;
run;

```

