12.2.3. Demography and Baseline Characteristics

Tables

No.	Population	IDSL No. / Example Shell	Title	Additional Programming Notes	Responsibility	Deliverable Priority
9.2	Safety	DM1	Summary of Demographic Characteristics	Include all variables collected.	Programmer	SAC, Group 3 SAC
9.3	Safety	DM5	Summary of Race and Racial Combinations		Programmer	SAC

Listings

No.	Population	IDSL No. / Example Shell	Title	Additional Programming Notes	Responsibility	Deliverable Priority
9.3	Safety	DM2	Listing of Demographic Characteristics	Include all variables collected.	Programmer	SAC, Group 3 SAC
9.4	Safety	DM9	Listing of Race		Programmer	SAC, Group 3 SAC

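### Age is named as a confounder of the resting HF-HV contrast, but a floor at 40 is the only analytic control: no age term, and no age summary in the primary set

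*SAP*

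**What the plan says.** SAP Section 5 gives the reason for changing the evaluable population: "At the interim analysis, it was realized that age may confound the results in the HV population". It continues: "Since HV and HF subjects were not age-matched, limiting the analysis population to similar age range will provide a more appropriate comparison". The rule is a lower limit at 40, with no upper limit, matching, stratification or weighting. It excludes 4 subjects. To make up numbers, "the study has enrolled an additional 5 subjects who are >40 years old in order to have a sufficient number of subjects for comparison".

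The eligibility rule for both groups, in Protocol 4.2.1.3, is "Males or females over 18 years of age at the time of signing the informed consent".

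The primary model in SAP 10.1.1 contains visit, group and their interaction: "model mriresn = visit atrtgrp visit*atrtgrp/e3 ddfm=kr outp=pred_one". The text of that section lists the same terms. Age is available for every subject under SAP 7.5: "Age will be calculated using the date of the screening visit relative to year of birth".

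On reporting, SAP 8.2 says "Demography data will be summarized for safety population in this study". The display list in 12.2.3 agrees: Table 9.2, "Summary of Demographic Characteristics", uses the safety population. The planned sensitivity analysis (Sections 5 and 5.1, Table 11.2) also uses the safety population, that is, all ages, with no age adjustment.

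**The concern.** The first primary objective is whether DCE-MRI separates HF patients from healthy volunteers at rest. That is a comparison of two non-randomised groups, and the sponsor itself regards age as a threat to it. If HF patients over 40 are older than volunteers over 40, and v_e or k^trans drifts with age, part of the estimated difference is an age effect. It could be read as evidence that the technique detects oedema or permeability change, and the study exists to judge whether the technique can serve as an endpoint in later drug studies.

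The plan also gives the reader no direct way to tell whether the restriction worked. No table shows age by group in the primary set. Comparing Table 11.1 with Table 11.2 shows the effect of dropping the under-40s, not any imbalance that remains above 40.

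**Working it through.** **Text.** Set side by side, the places agree with one another and leave the gap open. Section 5 names age and restricts on it. Section 10.1.1 does not adjust for it, in text or code. Section 8.2 and Table 9.2 do not describe it in the set that is analysed. The sensitivity analysis relaxes the restriction.

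**No figure to reproduce.** The documents give no ages, age slopes, SD, effect size or power; Protocol 8.2 bases the size on feasibility. What follows shows scale only, on assumed inputs.

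**Inputs.**
- Planned 12 + 12 = 24 (SAP Section 3). Less 4 excluded, plus 5 added (Section 5): 24 − 4 + 5 = 25. The split is not stated; 12 HF and 13 HV is assumed.
- Assumed: within-group age SD 9 years, residual SD 1, linear age effect, no true HF effect, one value per subject.

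**Formulas.**
- Bias of the unadjusted contrast = slope per decade × age gap / 10.
- SD about the group mean = √(1 + (0.9 × slope)²), since 9 years is 0.9 decade.
- Unadjusted SE = that SD × √(1/12 + 1/13) = SD × 0.400.
- RMSE = √(bias² + SE²).

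Example, gap 10 years, slope 0.4: bias = 0.4 × 1.0 = 0.40; SD = √(1 + 0.36²) = 1.063; SE = 0.425; RMSE = √(0.160 + 0.181) = 0.58. Simulation (6,000 trials per cell) gives bias 0.39 and RMSE 0.57.

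| Gap (y) | Slope (SD/decade) | Bias (SD) | 95% CI coverage | RMSE unadjusted | RMSE with age |
|---|---|---|---|---|---|
| 0 | any | 0 | 95% | | |
| 5 | 0.2 | 0.10 | 94% | 0.42 | 0.43 |
| 10 | 0 * | 0 | | 0.40 | 0.48 |
| 10 | 0.2 | 0.20 † | | 0.46 | 0.48 |
| 10 | 0.4 | 0.39 | 86% | 0.57 | 0.46 |
| 14 | 0 * | 0 | | 0.40 | 0.53 |
| 14 | 0.2 | 0.28 † | | 0.49 | 0.55 |
| 14 | 0.6 | 0.84 | 57% | 0.96 | 0.54 |

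\* Variant with ages truncated at 40 and an assumed HV mean age of 55. † From the bias formula. Blank cells were not tabulated.

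Truncating ages at 40 changes the other results little: at 10 years and 0.4, bias 0.37, coverage 87%, RMSE 0.56 against 0.47.

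**Precision cost of an age term.** Ratio of adjusted to unadjusted SE at slopes 0.2, 0.4 and 0.6:
- no gap: 1.01, 0.96, 0.90
- 5 years: 1.05, 1.00, 0.94
- 10 years: 1.17, 1.11, 1.04
- 14 years: 1.30, 1.25, 1.16

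**Shallower slopes.** With 12 against 12, the 95% CI half-width is t(0.975, 22) × √(2/12) = 2.074 × 0.408 = 0.85 SD. At a 10-year gap and slopes of 0.1 to 0.3, bias is 0.1 to 0.3 SD, and the interval excludes zero in 5.6% to 10.8% of studies with no HF effect (noncentral t), against 5% nominal.

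**Non-linear age effects,** 10-year gap, with 4 volunteers aged 20 to 39 added for the all-subjects analysis:
- Flat to 55, then 0.8 SD per decade: bias 0.61 unadjusted over 40 (coverage 76%), 0.02 adjusted over 40, 0.16 adjusted in all subjects.
- 0.4 SD per decade below 50, flat above: 0.05, 0.00 and −0.08. Here the cut has already done the work.

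**The case against.** The strongest case for the plan is that residual imbalance is conjecture. The documents report no ages; the sponsor restricted the range and then recruited 5 more subjects over 40; and if age matters only at younger ages, the cut is enough. The large biases need a wide gap and a steep slope. At 0.6 SD per decade with age SD 9, age would explain 0.54² / (1 + 0.54²) = 23% of within-group variance.

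Adjustment can also hurt. With about 12 per group, an age term raises RMSE when age matters little (0.40 to 0.48 at a 10-year gap and zero slope) and gives no gain at 0.2 SD per decade. The study is small and estimation-only. The exercise and repeatability objectives are within-subject and largely untouched, and the ADHF objective is separate. Ages in the evaluable set can be pieced together from Listings 9.1 and 9.3.

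Much of this stands. The size is unknown, the exposure is confined to the resting between-group contrast, and an unadjusted restricted comparison is defensible as the main result. It is a reason to put the adjusted estimate beside the unadjusted one rather than in its place. It does not remove the gap. The 5 additions were made for numbers, with no stated aim of balancing age. Estimation makes bias no less relevant, since the point estimate and interval are the product. A reader should not have to assemble the key balance check by hand.

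**Conclusion.** The concern holds and should be fixed. The SAP raises age confounding, restricts on a lower limit alone, leaves age out of the primary model and does not describe age in the primary set. A floor at 40 does not by itself balance ages above 40, so the HF-HV contrasts at Sessions 1 and 2 remain open to age confounding.

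This is a statement about exposure, not a demonstrated bias. The bias is zero if ages balance or if v_e and k^trans do not vary with age over 40. Under the assumed inputs it runs from 0.10 SD at a modest gap and slope to 0.39 SD at 10 years and 0.4 SD per decade. The 0.84 SD cell is an extreme. The near-zero bias after adjustment in the linear cells follows from assuming a linear effect with a common slope in both groups.

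**What to change.** 1. In SAP 10.1.1, add an analysis of v_e and k^trans in the over-40 set with centred age (as derived in 7.5) in the MODEL statement. Report the adjusted HF-HV contrasts at Sessions 1 and 2 next to the unadjusted ones. The existing ESTIMATE coefficients need no change.
2. Add a table of age by group in the evaluable population.
3. State that the age cut and the covariate were both chosen after the interim look.
4. Treat any age-adjusted analysis of all subjects as supportive only, because it may rest on extrapolation below 40.
5. Editorial: use one age cut (Section 5 has both 40 or above and strictly above 40). Align the three descriptions of the sensitivity analysis: change from baseline in v_e in Section 5, v_e in Section 5.1, and v_e with k^trans in Table 11.2. The resting contrast for both parameters is the one needed here.

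The cost is wording, one model term and one table, with no new data. The downside is precision: the SE changes by −10% to +1% with no age gap, and rises by 4% to 17% at 10 years and 16% to 30% at 14 years, least where the slope is steep. If age has little effect, the adjusted estimate will be the poorer of the two, so the report should show both.
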